### **7.0 PATIENT ENROLLMENT, DISPOSITION AND COMPLIANCE**

The number of patients in analysis populations (ITT, mITT, Safety, and PP) will be summarized for the overall study. The numbers and percentages of patients randomized by county and site will be presented. The numbers and percentages of patients who complete the study and the numbers and percentages of patients who prematurely discontinue the study will be presented overall and by analysis cycle defined in [Figure 11-1](#).

The study completers will be defined as the patients who received at least one study treatment and marked as completed in the eCRF disposition page. A patient who received study treatment in the relevant cycle will be considered to have completed the analysis cycle, if (a) the patient is a study completer or (b) the patient received the subsequent study treatment (Bim SR).

The categories of premature discontinuation reasons and the number of patients who prematurely discontinued during the study will be summarized.

### **8.0 DEMOGRAPHICS AND OTHER BASELINE DATA**

Demographics and other baseline characteristics will be summarized descriptively for the ITT population.

## **8.1 DEMOGRAPHICS**

Demographic parameters including age, age group, race, race group, ethnicity, sex as well as baseline characteristics such as weight (kg) and height (cm) will be summarized descriptively. Patient's age at Baseline (years) will be presented in categories of less than 45 years; between 45 years and 65 years, inclusive; and greater than 65 years. In addition, race will be further grouped as White versus non-White and Hispanic versus non-Hispanic (Ethnicity).

## **8.2 BASELINE CHARACTERISTICS**

Baseline characteristics for each eye will be descriptively summarized by treatment of the eye for the following categories: iris color, diagnosis of either OAG (primary OAG, pseudoexfoliation glaucoma, pigmentary glaucoma) or OHT, baseline Hour 0 IOP ( $\leq 25$  mm Hg or  $> 25$  mmHg), iridocorneal angle Shaffer grade, and central endothelial cell density, will be summarized descriptively by treatment group for the ITT population. Study eye iris color will be summarized by color for each of the following categories: monochromic, heterochromic peripupillary, and heterochromic diffuse.

## **8.3 MEDICAL AND SURGICAL HISTORY**

Abnormalities in patients' medical and surgical histories will be coded using the Medical Dictionary for Regulatory Activities (MedDRA), 21.0 or newer. The number and percentage of patients with non-ophthalmic medical and surgical histories at the time of randomization will be summarized separately by system organ class (SOC) and preferred term (PT) for the ITT population. Ophthalmic medical and surgical histories associated with Bim SR eye and SLT eye at randomization will also be summarized separately for the Safety Population by SOC and PT.

## **8.4 PRIOR AND CONCOMITANT MEDICATIONS**

Medications will be coded using the current version of World Health Organization Drug Global Dictionary and anatomical therapeutic chemical (ATC) classification system.

Prior medications are defined as medications with administration date or start date before the date of randomization. Concomitant medications are defined as those medications with administration date or start date on or after the date of the initial treatment. If a medication started prior to the date of randomization and continued past the date of randomization, it will be considered ongoing at randomization (i.e., study start) and will be presented as both a prior medication and a concomitant medication.

#### **8.4.1 General Medications**

Prior and concomitant non-ocular medications will be summarized by drug class and preferred name in the ITT population.

#### **8.4.2 Ocular Medications**

Prior ocular medications, washout ocular medications, concomitant ocular medications, and non-study IOP lowering medications will be summarized by eye identified by randomized treatment, drug class, and preferred name separately. A non-study IOP-lowering medication will be defined by the information provided by the investigator on electronic case report form (eCRF).

### **9.0 STUDY DURATION**

Patients' study duration will be summarized using descriptive statistics for each treatment group using safety population. Duration of time on study (days) for each patient will be calculated as the last visit date available or study exit date– Day 1 SLT administration date + 1.

### **10.0 EFFICACY ASSESSMENTS**

The primary efficacy measurement is IOP at Hour 0, which will be measured in each eye using the Goldmann applanation tonometer. Two consecutive measurements will be taken for each eye. If the first 2 measurements differ by  $> 1$  mm Hg, a third measurement will be taken. The IOP value for a given eye will be the median of all measurements, and this is consistent with the protocol IOP description in Study Protocol [Section 6.1.1](#) (If the first 2 measurements differ by  $\leq 1$  mm Hg, the IOP for the given eye will be the average of the 2 readings. If the difference between the first 2 measurements is  $> 1$  mm Hg, the IOP for the given eye will be the median of the 3 readings). For consenting patients at selected sites, additional IOP data will be collected at Hour 2 and 8, and these data will be included in [REDACTED].

#### **10.1 PRIMARY EFFICACY ANALYSIS**

The primary efficacy variable is Hour 0 IOP change from baseline (follow-up value minus baseline value, thus negative values reflect IOP reduction from baseline) assessed at Weeks 4, 12, and 24. Intraocular pressure values at Hour 0 at Baseline visit is considered as the baseline values.

Baseline and Weeks 4, 12 and 24 Hour 0 IOP measurements with their changes from baseline will be descriptively summarized.

Primary efficacy analysis will be performed for patients in the mITT population. The null and alternative hypotheses for the comparison between Bim SR treated eyes and SLT treated eyes at Weeks 4, 12, and 24 are:

- Null hypothesis: the difference in mean IOP change from baseline between the Bim SR and SLT eye (Bim SR minus SLT) is  $> 1.5$  mmHg.
- Alternative hypothesis: the difference in mean IOP change from baseline between the Bim SR eye and SLT eye (Bim SR minus SLT) is  $\leq 1.5$  mmHg.

Hour 0 IOP change from baseline will be analyzed using a mixed effect model for repeated measurement (MMRM). The model will include Hour 0 IOP change from baseline as the response variable and treatment, visit, eye, baseline Hour 0 IOP, treatment-by-visit, treatment-by-baseline Hour 0 IOP, treatment-by-eye, visit-by-eye interactions as covariates. Unstructured covariance matrix for study visit and compound symmetry correlation for eyes will be used for repeated measures on the same patient. If the model fails to converge, alternative covariance structures may be used in the MMRM analysis. If the model fails to converge with alternative covariance structures, multiple imputation (MI) will be implemented before MMRM.

The mean difference in the Hour 0 IOP change from baseline between the Bim SR eyes and SLT eyes (Bim SR minus SLT) in the mITT population and the corresponding 95% confidence intervals (CI) will be constructed at each visit from MMRM analysis. The noninferiority comparison for Bim SR versus SLT at Weeks 4, 12, and 24 is the primary analysis. If the upper limit of the 95% CI is  $\leq 1.5$  mmHg at all 3 visits, Bim SR 15  $\mu$ g statistical noninferiority to SLT is considered demonstrated.

For additional clinical consideration, Bim SR is considered clinically noninferior to SLT if the upper limit of the 95% CI is  $\leq 1.0$  mmHg at 2 out of the 3 visits of Weeks 4, 12, and 24.

Sample SAS® code for primary analysis is shown as below:

```
proc mixed data=iop4;
  where avisitn >1;
  class subjid eye trt avisitn;
  model chg=trt avisitn eye base trt*avisitn
        trt*base trt*eye avisitn*eye/ddfm=kr;
  repeated avisitn*eye/type=un@cs subject=subjid rcorr;
  lsmeans trt*avisitn/diff;
run;
```

The definitions of variables are:

chg = Hour 0 IOP percentage change from baseline at the primary analysis time points of Week 4, Week 12, and Week 24

avisitn = Programming derived analysis visits at Week 4, Week 12, and Week 24

subjid = Subject ID

eye = Variable to indicate primary eye or contralateral eye

trt = Variable to indicate Bim SR treatment or SLT treatment

base = Baseline IOP

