7.3.1 Primary Efficacy Analyses

The primary efficacy analysis will be performed for patients in the mITT population. The primary efficacy variable is IOP change from baseline and Weeks 4, 12, and 24 are the primary analysis timepoints.

The null and alternative hypotheses for the comparison between Bimatoprost SR 15 µg treated eyes and SLT treated eyes at each visit of Weeks 4, 12, and 24 are:

- Null hypothesis: the difference in mean IOP change from baseline between the Bimatoprost SR 15 µg and SLT eye (Bimatoprost SR minus SLT) is > 1.5 mm Hg.
- Alternative hypothesis: the difference in mean IOP change from baseline between the Bimatoprost SR 15 µg eye and SLT eye (Bimatoprost SR minus SLT) is ≤ 1.5 mm Hg.

IOP change from baseline will be analyzed using a mixed effect model for repeated measures (MMRM). The model will include IOP change from baseline as the response variable and treatment, visit, eye, baseline IOP, treatment-by-visit, treatment-by-baseline, treatment-by-eye, and visit-by-eyes interactions as covariates. Unstructured correlation for study visits and compound symmetry correlation for eyes will be used for repeated measures on the same patient; if the model fails to converge, multiple imputation (MI) will be implemented before MMRM.

The mean difference between the Bimatoprost SR 15 µg eyes and SLT eyes (Bimatoprost SR 15 µg minus SLT) in the mITT population and the corresponding 95% confidence interval (CI) will be constructed at each visit from MMRM analysis. The noninferiority comparison for Bimatoprost SR 15 µg versus SLT at Weeks 4, 12, and 24 is the primary analysis. If the upper limit of the 95% CI is ≤ 1.5 mm Hg at all 3 visits Bimatoprost SR 15 µg statistical noninferiority to SLT is considered demonstrated. In addition, Bimatoprost SR 15 µg is considered clinically noninferior to SLT if the upper limit of the 95% CI is ≤ 1.0 mm Hg at 2 out of the 3 visits of Weeks 4, 12, and 24.

As part of the sensitivity analysis for the primary efficacy analysis, a PP analysis using the same MMRM model as the one used in the primary efficacy analysis will be performed. The PP analysis will be based on the data from PP population.

Additionally, a by-visit analysis using an ANCOVA model will be conducted using the data from ITT population, where the between-eye correlation will be included in the same way as the MMRM model used for the primary analysis.

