## **14.0 DETERMINATION OF SAMPLE SIZE**

The sample size calculation is based on paired-eye differences using a normal approximation with a 2-sided significance level of 0.05, assuming that there is no difference in mean IOP change from baseline between Bim SR eyes and SLT eyes, and that change from baseline in IOP has a standard deviation of 4 mmHg. A sample size of 144 patients will provide approximately 98% power in showing noninferiority in 3 out of 3 timepoints with a noninferiority margin of 1.5 mmHg, and 90% power in showing noninferiority in 2 out of 3 timepoints with a noninferiority margin of 1.0 mmHg, assuming that both the between-eyes and the within-patient correlation coefficients are 0.5.

Assuming a premature discontinuation rate of 10%, approximately 160 patients are to be enrolled into this study.

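### The clinical noninferiority verdict (upper limit at most 1.0 mm Hg at two of three visits) does not depend on the primary test, so it can be awarded after that test fails

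*SAP*

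**What the plan says.** SAP 10.1 and Protocol 7.3.1 define two verdicts from the same visit-specific confidence intervals.

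- **Statistical noninferiority.** If the upper limit is at most 1.5 mm Hg at all three visits, "statistical noninferiority to SLT is considered demonstrated" (Protocol 7.3.1). This is the only rule with a stated null and alternative hypothesis.
- **Clinical noninferiority.** The SAP continues: "For additional clinical consideration, Bim SR is considered clinically noninferior to SLT if the upper limit of the 95% CI is" at most 1.0 mm Hg at two of the three visits. Protocol 7.3.1 has the same rule: Bimatoprost SR "is considered clinically noninferior to SLT if the upper limit of the 95% CI is" at most 1.0 mm Hg at two of three. The Protocol Summary repeats it.

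None of the three places makes the second verdict depend on the first, limits the remaining visit, or says what is concluded when the two disagree. The superiority test is treated differently: SAP 10.2 and Protocol 7.3.2 allow it only after noninferiority has been shown.

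SAP 14.0 gives the clinical rule its own power, "90% power in showing noninferiority in 2 out of 3 timepoints with a noninferiority margin of 1.0 mmHg", alongside about 98% for the primary rule. It gives no power for meeting both.

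**The concern.** A margin of 1.0 mm Hg sounds more demanding than 1.5 mm Hg, and a reader would expect the clinical verdict to be the harder one to reach. It is harder at the two visits that count, but it ignores the third. The primary rule requires all three visits precisely so that a poor result at one of them blocks the claim, and the clinical rule discards that protection.

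Upper limits of 0.9, 0.9 and 3.0 mm Hg, for example, fail the primary rule and satisfy the clinical one. The report could then state, in line with the plan, that noninferiority was not demonstrated and that the product is clinically noninferior. Because the rule sits in the primary analysis section, is worded as a verdict and is separately powered for showing noninferiority, it is likely to be read as a noninferiority claim in its own right.

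**Working it through.** **Inputs, all from SAP 14.0:**

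- two-sided 5% level, normal approximation
- true difference of zero at every visit
- 144 patients
- per-eye SD of the IOP change: 4 mm Hg
- correlations: "both the between-eyes and the within-patient correlation coefficients are 0.5"

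**Standard error.** SD of the paired difference = 4 × √(2 × (1 − 0.5)) = 4 mm Hg. SE = 4/√144 = 0.333 mm Hg. Upper limit = estimate + 1.96 × 0.333 = estimate + 0.653. A visit therefore passes at 1.5 if its estimate is at most 0.847, and at 1.0 if its estimate is at most 0.347.

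**Reproducing the plan's power.** Per-visit power at zero difference is Φ(margin/SE − 1.96):

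- margin 1.5: Φ(4.5 − 1.96) = 99.4%
- margin 1.0: Φ(3.0 − 1.96) = 85.1%

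Treating the three visit estimates as trivariate normal with correlation 0.5 gives 98.5% for three of three at 1.5 (stated: about 98%) and 88.9% for at least two of three at 1.0 (stated: 90%). With uncorrelated visits the figures would be 98.3% and 94.0%, so correlation 0.5 is the version that fits both stated values.

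**How often the verdicts conflict.** Same model, N = 144. Only the first row is the plan's assumption; the other rows are our illustrations.

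| True difference at the three visits (mm Hg) | Statistical | Clinical | Clinical without statistical | Both (gated rule) |
|---|---|---|---|---|
| 0, 0, 0 | 98.5% | 88.9% | 0.26% | 88.7% |
| 0.5, 0.5, 0.5 | 69.4% | 29.4% | 0.8% | 28.6% |
| 0, 0, 0.5 | 84.7% | 78.0% | 6.5% | 71.4% |
| 0, 0, 1.0 | 32.3% | 75.9% | 45.9% | 30.0% |
| 0, 0, 1.5 | 2.5% | 75.9% | 73.4% | 2.5% |

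Share of clinical verdicts that would follow a failed primary test in the last three rows: 6.5/78.0 = 8%, 45.9/75.9 = 60%, 73.4/75.9 = 97%.

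**Sensitivity to sample size.** Amendment 3 stopped enrolment and the mITT population excludes some patients, so the analysed number may be below 144. For assumed N of 80, 100 and 120, the conflict probability is 2.2%, 1.2% and 0.6% with no difference at any visit, and 43%, 54% and 64% with differences 0, 0 and 1.5.

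**Effect of gating.** Under the planning assumptions, power for the clinical verdict goes from 88.92% to 88.66%, a loss of 0.26 points.

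**The case against.** The best defence is that the clinical rule is a supplement. It follows the primary rule directly, both documents introduce it as something additional, it has no hypothesis of its own, it is not among the secondary analyses, and nothing else is gated on it. One may naturally read it as a further descriptor of a result already shown. Superiority cannot be reached falsely through it, because superiority needs an upper limit below zero at all three visits. Confidence intervals are reported for every visit, so a failed visit would be visible.

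The size is also open to challenge. Conflict is below 1% under the plan's assumption and under an equal 0.5 mm Hg difference. The large figures need one visit to depart from the other two, and the documents do not expect that: Protocol 1.2.3 reports similar efficacy after a second administration, and Week 24 falls eight weeks after the Week 16 implant. In those cases two visits truly have no difference, so the clinical verdict is correct by its own definition and the 97% is not an error rate.

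Most of this stands as a limit on weight. It does not close the gap. An introductory phrase is not a condition, and the authors wrote an explicit one for superiority. Separate power for showing noninferiority also goes beyond a purely descriptive remark. The ambiguity has to be settled in words, and doing so before the results are known is what gives the answer value.

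**Conclusion.** The concern holds. As written, the plan can award clinical noninferiority after the primary noninferiority test has failed, because the 1.0 mm Hg rule is unconditional and leaves one visit unconstrained.

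The consequence is a misleading label. The primary conclusion and its type I error are not affected, and neither is the superiority test. The expected frequency is about 0.3% under the planning assumptions. It becomes large (46% to 73%) only if one visit truly differs by 1.0 to 1.5 mm Hg while the other two show no difference, a pattern chosen here to show how the rule behaves and not one the documents predict. The figures rest on a normal approximation with known variance, not on the MMRM itself. This is a cheap improvement that should be made; it does not undermine the primary analysis.

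**What to change.** Add one sentence to SAP 10.1, Protocol 7.3.1 and the Protocol Summary: *Clinical noninferiority will be assessed only if statistical noninferiority (upper limit at most 1.5 mm Hg at all three visits) is demonstrated.* If the primary test fails, the visit-specific limits can still be shown against 1.0 mm Hg descriptively, without the verdict.

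The cost is that clinical noninferiority can no longer be claimed after a failed primary test, plus the 0.26 points of power shown above. No data collection, model or margin changes. If the condition was always intended, writing it down costs nothing.

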## 10.2 SECONDARY ANALYSIS

### Superiority test of Bim SR 15 µg versus SLT

As the secondary efficacy analysis, a superiority test of Bim SR 15 µg versus SLT will be performed if noninferiority is demonstrated in the primary efficacy analysis. Superiority of Bim SR versus SLT is considered achieved if the upper limit of the 95% CI is < 0 mm Hg at Weeks 4, 12, and 24. The mITT population will be used.

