**10.3 OTHER EFFICACY ANALYSES**

#### 10.4 SENSITIVITY ANALYSES

As part of the sensitivity analyses, the mean difference and 95% CI in the IOP change from baseline between the Bim SR eyes and SLT eyes (Bim SR minus SLT) will be constructed for each analysis visit for the Per Protocol (PP) population using the same MMRM model as the one used in the primary analysis.

To simplify the interpretation of treatment effect, and to allow flexible adjustment for baseline effect and the between-eye correlation across different visits, the following MMRM model will be used in sensitivity analysis using mITT population: (1) the MMRM model will include Hour 0 IOP change from baseline as the response variable and treatment, visit, eye, baseline Hour 0 IOP, treatment-by-visit, visit-by-baseline Hour 0 IOP, and visit-by-eye interactions as covariates; (2) an unstructured covariance matrix (6×6 matrix) will be used for measurements across 3 primary visits (Weeks 4, 12, and 24) and 2 eyes for the same patients. The same MMRM model will be used in the tipping-point sensitivity analysis described in the later part of the section.

Sample SAS® code for the sensitivity analysis is shown as below:

```
proc mixed data=iop4;
  where avisitn >1;
  class subjid eye trt avisitn repid;
  model chg=trt avisitn eye base trt*avisitn
        avisitn*base avisitn*eye/ddfm=kr;
  repeated repid/type=un subject=subjid rcorr;
  lsmeans trt*avisitn/diff;
run;
```

The definitions of variables are:

chg = Hour 0 IOP percentage change from baseline at the primary analysis time points of Week 4, Week 12, and Week 24

avisitn = Programming derived analysis visits at Week 4, Week 12, and Week 24

subjid = Subject ID

eye = Variable to indicate primary eye or contralateral eye

trt = Variable to indicate Bim SR treatment or SLT treatment

base = Baseline IOP

repid=Variable created to identify the repeated measures cross each eye and each visit within a given subject for the unstructured covariance matrix ( $6 \times 6$ ).

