Additionally, ANCOVA including within-subject correlation at each visit will be conducted using the observed values of ITT population, where IOP measurements obtained after initiating the use of non-study IOP-lowering medication will be set to missing. At each visit, the model for IOP change from baseline is specified as: IOP Change from Baseline = Treatment + Eye + Baseline IOP, where Eye is primary eye or contralateral eye. A compound symmetric covariance matrix will be used for between eye correlation.

The tipping-point sensitivity analysis will also be used to assess the robustness of the analysis results. A multiple imputation (MI) will be performed to the missing data as the first step; then different shifts using various assumptions on the missing IOP CFB will be applied to the imputed missing values in Bim SR treated eyes separately (note: shift will not be applied to SLT treated eyes); finally MMRM analyses will be conducted based on the imputed data with shifts and the corresponding tipping region of the shifts will be used to evaluate the robustness of the noninferiority conclusion.

In the MI procedures, a two-step method will be used to impute the missing values at Weeks 4, 8, 12, 15, 20, and 24 for each eye. During Step 1, missing intermittent data will be imputed to obtain a monotone missing pattern and during Step 2 linear regression will be used to impute the remaining missing values. Note that baseline IOP values associated with each eye must not be missing in any of the patients; otherwise they will be excluded from this analysis. At least twenty-five (25) sets of imputed datasets will be created using SAS proc MI procedure. A sample code is shown below for Hour 0 IOP measurements associated with each eye:

```
proc mi data=iop nimpute=25 seed=123451 out=_miint;  
  var baseline week4_hr0 week8_hr0 week12_hr0 week15_hr0 week20_hr0 week24_hr0;  
  by treatment;  
  mcmc chain=single impute=monotone;  
run;  
  
proc mi data=_miint nimpute=1 seed=123457 out=mifull;  
  class race_group sex lens;  
  var race_group sex lens age baseline week4_hr0 week8_hr0 week12_hr0 week15_hr0 week20_hr0  
  week24_hr0;  
  monotone regression (week4= race_group sex lens age baseline/details);  
  monotone regression (week8= race_group sex lens age baseline week4/details);  
  monotone regression (week12= race_group sex lens age baseline week4 week8/details);  
  monotone regression (week15= race_group sex lens age baseline week4 week8 week12/details);  

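### SAP 10.1 and 10.4 define the model response under the sample code as percentage change, but the prose specifies change from baseline and the margins are in mm Hg

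*SAP*

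**What the plan says.** SAP 10.1 defines the primary variable as the follow-up value minus the baseline value. For the mixed model it states: "The model will include Hour 0 IOP change from baseline as the response variable". The hypotheses are framed around 1.5 mm Hg, statistical noninferiority requires an upper 95% limit of at most 1.5 mm Hg at Weeks 4, 12 and 24, and clinical noninferiority requires at most 1.0 mm Hg at two of those visits. Protocol 7.2.1 and 7.3.1 agree.

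The sample PROC MIXED code in SAP 10.1 has `chg` on the left of its model statement, and the list below the code defines it: "chg = Hour 0 IOP percentage change from baseline at the primary analysis time points of Week 4, Week 12, and Week 24".

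SAP 10.4 repeats the pattern for the sensitivity model with a 6×6 unstructured covariance matrix. The prose says "the MMRM model will include Hour 0 IOP change from baseline as the response variable", while the definition of `chg` under the code is again percentage change. SAP 10.4 then adds: "The same MMRM model will be used in the tipping-point sensitivity analysis described in the later part of the section". The shifts in that analysis are described as "different shifts using various assumptions on the missing IOP CFB". The by-visit ANCOVA in the same section is written as "IOP Change from Baseline = Treatment + Eye + Baseline IOP" and carries no percentage definition.

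The superiority rule in SAP 10.2 is "upper limit of the 95% CI is < 0 mm Hg at Weeks 4, 12, and 24", and SAP 14.0 assumes that "change from baseline in IOP has a standard deviation of 4 mmHg".

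**The concern.** The definitions under the code are the only place where the SAP tells a programmer what the variable `chg` contains, and in both places they name a different quantity from the text they illustrate. In 10.1 the conflict is with the stated endpoint, the hypotheses and both margins. In 10.4 it is narrower: that section gives no margin and no unit, so its prose conflicts with its definition only on change versus percentage change.

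If the definition were followed, the primary treatment difference and its confidence limits would be in percentage points. No fixed percentage equals 1.5 mm Hg across patients, so the noninferiority rule could not be applied to that output. If 1.5 and 1.0 were applied anyway, the limits would be several times tighter than planned, and noninferiority would be harder to show. The superiority limit of zero does not tighten with a change of scale, so that test would be affected mainly because it is conditional on noninferiority. The tipping-point shifts, described on IOP change from baseline, would not match a percentage response.

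**Working it through.** **Inputs.** From SAP 14.0: SD of change 4 mm Hg, between-eye and within-patient correlations both 0.5, true difference 0, two-sided 0.05, 144 patients, margins 1.5 and 1.0 mm Hg, stated power about 98% and 90%, 10% discontinuation. From SAP 4.0: baseline Hour 0 IOP of 22 to 34 mm Hg in each eye.

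**Step 1: the plan's own figures, in mm Hg.**
- SD of the paired-eye difference = √(2 × 16 × (1 − 0.5)) = 4 mm Hg; SE = 4/√144 = 0.333.
- Power at one visit = Φ(margin/SE − 1.96). At 1.5: Φ(4.50 − 1.96) = Φ(2.54) = 99.4%. At 1.0: Φ(3.00 − 1.96) = Φ(1.04) = 85.1%.
- Joint power from a trivariate normal with correlation 0.5 between visits: all three visits at 1.5 = 98.5%. At least two of three at 1.0 = 3 × P(two given visits pass) − 2 × P(all three pass) = 88.9%.
- Enrolment: 144/(1 − 0.10) = 160.

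The stated 98%, 90% and 160 are reproduced, so the design rests on absolute change in mm Hg.

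**Step 2: what the margins mean in percent.** 1.5 mm Hg is 150/22 = 6.8% of a baseline of 22 and 150/34 = 4.4% of a baseline of 34. Conversely, 1.5 percentage points is 0.015 × 22 = 0.33 mm Hg to 0.015 × 34 = 0.51 mm Hg, which is 4.5 to 2.9 times tighter than the planned margin.

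**Step 3: the definition taken literally, with the limits 1.5 and 1.0 applied to the percentage output.** The documents give no SD for percentage change. As an assumption, SD% = 400/baseline, with one common baseline for all eyes; SE% = SD%/√144.

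| Baseline (mm Hg) | SD (%) | SE (points) | 95% CI half-width (points) | Power, 3 of 3 at 1.5 | Power, 2 of 3 at 1.0 |
|---|---|---|---|---|---|
| 22 | 18.2 | 1.515 | 2.97 | about 4% | 6% |
| 25 | 16.0 | 1.333 | 2.61 | 5% | 8% |
| 28 | 14.3 | 1.190 | 2.33 | 7% | 9% |
| 34 | 11.8 | 0.980 | 1.92 | 12% | 13% |

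**Step 4: the largest point estimate that passes a visit at 1.5.**
- In mm Hg: 1.5 − 1.96 × 0.333 = +0.85 mm Hg.
- In percentage points at baseline 22: 1.5 − 2.97 = −1.47 points, or −0.32 mm Hg.
- At baseline 25: 1.5 − 2.61 = −1.11 points, or −0.28 mm Hg.
- At baseline 34: 1.5 − 1.92 = −0.42 points, or −0.14 mm Hg.

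The half-width exceeds 1.5 throughout the range, so an observed difference of exactly zero would not pass a visit.

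**Step 5: is the conflict resolved elsewhere?** The visible text of the SAP amendment list (19.1) records no move to a percentage endpoint. SAP 10.3 is not in the public text, so it cannot be checked whether the wording was carried over from a percentage analysis there.

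**The case against.** The strongest reply is that nobody reading the whole plan could mistake the endpoint. The prose, hypotheses, margins, superiority limit, sample size and protocol all point to mm Hg, and the only dissent is one word in the definitions for code labelled as a sample. Harm needs two successive mistakes: coding to the definition against the prose, then comparing percentage points with mm Hg limits. The first should be noticed. Protocol 1.2 cites reductions of 7 to 8 mm Hg from a mean baseline of 26 with topical bimatoprost, which on a percentage scale is about 27% to 31% (7/26 and 8/26). SAP 10.1 also requires descriptive summaries of IOP and its changes at the same visits. The sample multiple-imputation code appears to work on IOP values, which again suggests an absolute scale. Table specifications sit in a separate document, so it is unknown whether any dataset carries the error.

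Most of this stands. It makes this a drafting error with a recoverable meaning, not a deliberate choice of a percentage endpoint. It also limits the power figures: they describe a misread output, rest on an assumed SD, and have as end points the eligibility limits for individual eyes, which a whole trial would not sit at. It does not make the two definitions correct.

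**Conclusion.** The concern holds. The code-level definition of the primary response in SAP 10.1 contradicts the endpoint, hypotheses and margins in the same section. The same definition in SAP 10.4 contradicts that section's prose for a sensitivity model that is also named for the tipping-point analysis. The intended scale is absolute change in mm Hg, and on that scale the stated power and sample size hold.

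The certain consequence of following the definition is an interval that cannot be compared with the margins. The loss of power to about 4% to 12% (three of three visits at 1.5) and 6% to 13% (two of three at 1.0) depends on the output then being compared with the unchanged limits, and on the assumed SD. The direction is against Bimatoprost SR, so a false noninferiority claim is not the risk. This should be corrected, but it does not undermine the design.

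**What to change.** In the definitions under the sample code in SAP 10.1 and SAP 10.4, delete the word percentage and define `chg` as *Hour 0 IOP change from baseline in mm Hg (visit value minus baseline value)*. Before database lock, check that the analysis-dataset specification derives `chg` the same way.

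The cost is one line in each of two places and one check of a specification. Design, margins and sample size do not change.
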